12.2.3 Adverse Event/Serious Adverse Event Recording

¹⁷ For females of childbearing potential, serum pregnancy test completed within 3 days prior to Day 1 of Cycle 1.

¹⁸ For females of childbearing potential. This is only required if patients are receiving drug.

²⁰ IgHV to be done at screening if mutation status is not already known.

¹⁹ Baseline BM as clinically indicated as per standard of care. Post-baseline BM biopsy to confirm potential CR required.

²¹ FISH central lab results required for randomization. Samples for FISH, and NGS to be sent to the Central Lab, see lab manual for sample collection and shipment procedures.

²² MRD in peripheral blood at baseline and Cycle 6, Cycle12, Cycle 15 and Cycle 24 (MRD drawn only if subject is in PR or better). One MRD by bone marrow aspirate sample should be completed for all patients MRD negative by peripheral blood. Thereafter, all subjects without signs of clinical progression, repeat MRD every 6 cycles (peripheral blood). Subjects that end treatment prior to Cycle 15 should continue to have MRD collected until month 15. See laboratory manual for collection, processing, and shipment instructions.

²³ A total of 2 serum samples should be collected from each subject for sparse population PK analyses (Pre-dose on Cycle 4, Day 1, and one randomly assigned post-baseline sample). See Section7.2.1 Sparse Sampling **Pharmacokinetics**

²⁴ Samples to be collected pre-dose of ublituximab

²⁵ Response assessment at baseline (within 30 days prior to Cycle 1 Day 1), and within 14 days prior to Cycles 4 & 12, and at least every 6 cycles thereafter. Radiologic assessment should include CT with contrast or MRI imaging of neck, chest, abdomen, and pelvis. BM biopsy to confirm potential CR required. If PD is suspected, scans and relevant clinical data should be sent to central radiology for expedited PD review. This PD confirmation should be obtained prior to subject being removed for PD (except in rare cases where it is in the patients best interest to be discontinued immediately.

²⁶ Venetoclax Cohort Only: TLS risk assessment according to Section 8.5.3.1 at baseline and on Day 1 of Cycle 4, prior to first dose of venetoclax.

27 AEs are to be reported from Cycle 1 Day 1 and SAEs are to be reported from signing of informed consent. A 30-day (± 7 days) and a 90-day (± 7 days) safety follow up visit is required after the last dose of study drug. See Section

Dated: 05 October 2021 (Ver 4.0) U2-VEN-207

Cycle = 28 days	Screening ¹		Cyc	Cycle 12		Cycles		Cyc	Cycle 44		Cycles	Cycles	Cycle	EOT	30-and	LTFU7	EOS,8
)		•			$2-3^{3}$		•			5&63	9, 12,	18 and		90-Day		
												155	63		Safety		
													Cycle		FU6		
Procedure/Days	D-30 to D0 D1 D2 D8	D1	D2	9G	D15	D1	D1	8G	D15	D22	D1	D1	D1				
Pre-authorization	X																
for venetoclax (if																	
applicable)																	
Randomize	D-7 to D1																
								Arm A	n A								
Venetoclax								Oral	ly daily	*see ramp	Orally daily *see ramp-up schedule	е					
Ublituximab		X	X	X	X	X	X				X	X					
Umbralisib		X28	X				Orally	once da	Orally once daily with food	pood							
								Arn	Arm B								
Ublituximab		X	X	X	X	X	X				X	X	X				
Umbralisib		X28	×					Orally or	nce dailt	Orally once daily with food	7						

28 Umbralisib will be self-administered (by the subject). On Cycle 1 Days 1 and 2, when ublituximab will be administered, umbralisib should be administered prior to ublituximab pre-medication.

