			mg daily 400 mg daily					

U2-VEN-207

Cycles 7 - 15					
Ublituximab Umbralisib Venetoclax					
Day 1 of Cycle 9, Cycle 12, and Cycle 15	Days 1 - 28	Days 1 - 28			
900 mg	800 mg daily	400 mg daily			

Phase 3: Arm B (U2) Randomized Subjects					
	Cycle 1				
Ublituximab			Umbralisib		
Day 1	Day 2	Day 8 & 15	Days 1 - 28		
150 mg	750 mg	900 mg	800 mg		
	Cycles 2 - 6				
1	Jblituximab	Umbralisib			
Day 1			Days 1 - 28		
900 mg		800 mg			
	Cycle 7+				
Ublituximab			Umbralisib		
Day 1, every 3 cycles (9, 12, 15, 18, etc.)		Days 1 - 28			
900 mg		800 mg			

Study Drugs

Ublituximab is an investigational, recombinant chimeric monoclonal antibody against the CD20 antigen, available as a 25 mg/mL concentrate for solution for infusion, supplied by TG Therapeutics, Inc.

Umbralisib is a novel investigational, once daily oral dual inhibitor of PI3K δ and CK1 ϵ available in 200 mg tablets, supplied by TG Therapeutics, Inc.

Venetoclax is an orally administered BCL-2 inhibitor available in 10 mg, 50 mg, and 100 mg tablets, commercially available as VENCLEXTATM.

LIST OF ABBREVIATIONS

Abbreviations and Definitions of Terms				
ADCC	antibody-dependent cellular cytotoxicity			
ADCP	antibody-dependent cellular phagocytosis			
ADL	activities of daily living			
AE(s)	adverse event(s)			
AESI	adverse event of special interest			
AKT	protein kinase B			
ALC	absolute lymphocyte count			
ALT	alanine aminotransferase			
AST	aspartate aminotransferase			
ATP	adenosine triphosphate			
AUC	area under the curve			
BCG	Bacille Calmette Guerin			
BCL-2	B-cell lymphoma 2			
ВН	BCL-2 homology			
BM	bone marrow			
BTK	bruton's tyrosine kinase			
BUN	blood urea nitrogen			
C, c	Cycle			
Ca	calcium			
CBC	complete blood cell count			
CD	cluster of differentiation			
CDC	complement-dependent cytotoxicity			
CK1E	casein kinase 1 epsilon			
CL	clearance			
CLL	chronic lymphocytic leukemia			
Cm	centimeter			
Cmax	maximum concentration			
CMV	cytomegalovirus			
CNS	central nervous system			
CO ₂	carbon dioxide			
CR	complete response			
CRi	complete response incomplete			
CRO	Contract Research Organization			
CT	computed tomography			
CTCAE	Common Terminology Criteria for Adverse Events			
CVA	cerebrovascular accident			
D, d	day/Day			
DLBCL	diffuse large B-cell lymphoma			
DLT	dose limiting toxicity			
DNA	deoxyribonucleic acid			
DOR	duration of response			
DRG	data review group			
DSMB	Data Safety Monitoring Board			
EC	ethics committee			

U2-VEN-207

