During the study period, all subjects will be evaluated for response by CT and/or MRI. At each follow-up visit, subjects will be assessed for response/progression by physical examination and laboratory tests. The best clinical response as well as disease progression will be determined by an IRC. Subjects will remain on study treatment until the occurrence of definitive disease progression (subjects enrolled to the randomized Phase 3 stage must have PD confirmed by central radiology prior to discontinuing study drug), completion of treatment, unacceptable toxicity, or withdrawal from the study due to Investigator decision or other reasons. Subjects who discontinue from study treatment (either for unacceptable toxicity or Investigator choice) and have not progressed will continue to be followed for progression until confirmed by IRC. All subjects enrolled to the Phase 3 portion of the study will be followed for overall survival.

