the study drugs and is not going into LTFU. 9 Heart rate, blood pressure, temperature, respirations.

¹⁰ Hematology and chemistry must be done prior to ublitaximab administration.

¹¹ See Section 8.5.3: Guidelines for Administration of Venetoclax for dose ramp-up schedule and recommended blood chemistry monitoring based on tumor burden.

¹² Cycle 4, day 8, 15 and 22 only required for patients receiving venetoclax and during the venetoclax ramp-up.
13 PT/INR to be done at screening and as clinically indicated. INR should be monitored closely in subjects receiving venetoclax and warfarin.

¹⁴ Serum virology to include HBsAg, HBcAb and HCV AB. If HBcAb is positive subjects must be evaluated for the presence of active HBV by PCR. If HCV AB positive, subjects must be evaluated for the presence of HCV by

¹⁵ At baseline, CMV IgG and IgM or CMV by PCR (if institutions SOC). Thereafter, CMV by PCR for all subjects while receiving umbralisib beginning C4D1, then C6D1 and approximately every 3 cycles thereafter up to Cycle

^{24,} then approximately every 6 cycles thereafter. If CMV IgM or IgG is positive, subjects must be evaluated for the presence of active CMV by PCR U2-VEN-207

	_		_			_		_	_	_		_	_				
E0S,8														X			X
LTFU7											X			X			
30-and 90-Day Safety FU ⁶																×	
EOT																×	×
Cycle 18 and Q3 Cycle ⁵	D1	C24									C24			X25		X	X
Cycles 9, 12, 15s	D1	C12			X						C12 and C15		C12	X25		X	X
Cycles 5&6 ³	D1				X						90		90			×	X
	D22															×	
Cycle 44	D15															×	
Cyc	8Q															×	
	D1				X							X		X	×	×	X
Cycles 2-33	D1				X								E)			X	X
	D15												X			×	X
Cycle 1 ²	8Q															×	X
Č	D2															×	X
	D1												X			×	X
Screening ¹	D-30 to D0	X	X	X		X19		X	X^{20}	X	X			X	X	×	
Cycle = 28 days	Procedure/Days	Quant IgG, IgA, IgM16	β ₂ -microglobulin	Serum Pregnancy Test ¹⁷	Urine Pregnancy ¹⁸	BM	biopsy/aspirate	EKG	AH9I	FISH and NGS ²¹	MRD ²²	Sparse PK ²³	Immunogenicity ²⁴	Response Assessment ²⁵	TLS Risk- Assessment ²⁶	AE Assessment ²⁷	Con Med Assessment

¹⁶ To be completed at baseline, during Cycle 12, and during Cycle 24 only.

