7 LABORATORY ASSESSMENTS

Laboratory assessments will be collected as specified in the study assessments tables. Please see Section 8.5.3.1 for details regarding recommended blood chemistry monitoring based on tumor burden.

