11.11 STATISTICAL ANALYSES

11.11.1 PRIMARY EFFICACY VARIABLES

11.11.1.1 PROGRESSION-FREE SURVIVAL (PHASE 3)

PFS is defined as the number of days between randomization and the date of progression (as confirmed by the IRC) or death due to any cause, whichever occurs first. Subjects who had no event (progression or death) will be censored at the day of their last adequate disease assessment. If no baseline or post-baseline assessment is available, the subject will be censored at the date of randomization. If death or PD occurs after 2 or more consecutive missing disease assessments, censoring will occur at the date of the last adequate disease assessment prior to the missed assessments. The use of a new anticancer therapy prior to the occurrence of PD will result in censoring at the date of last adequate disease assessment prior to initiation of new therapy.

Hypothesis testing for comparison between the treatment arms will be performed using a stratified (by randomization stratification factors) log-rank test via SAS Lifetest procedures. For each treatment arm, the median duration of PFS and the proportion of subjects alive and progression-free at 6, 12, 24, and 36 months will be estimated using the Kaplan-Meier method. For each estimate, a 95% confidence interval will be reported. The hazard ratio with 95% confidence interval will be estimated by stratified (by randomization stratification factors) Cox proportional hazards model.

U2-VEN-207

Sensitivity analyses will be conducted, including using investigator assessment of PFS, using different censoring rules (ignoring new anti-cancer therapy, ignoring 2 or more consecutive missing assessments). In addition, the potential impact of COVID-19 on patients for the efficacy results may be included in the sensitivity analysis (censoring all subjects at the last adequate assessment if subject discontinued study or death due to COVID-19). Other sensitivity analyses may be conducted as needed.

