12.8 PREGNANCY

Pregnancy, Abortion, Birth Defects/Congenital Anomalies

During the study, all female subjects of child-bearing potential (the definition of females of child-bearing potential are listed in Appendix A - Contraception Guidelines) must contact the treating Investigator immediately if they suspect that they may be pregnant (a missed or late menstrual period should be reported to the treating Investigator).

If an Investigator suspects that a subject may be pregnant prior to administration of study drug(s), the study drug(s) must be withheld until the result of the pregnancy test is confirmed. If a pregnancy is confirmed, the subject must not receive any study drug(s) and must be discontinued from the study.

If an Investigator suspects that a subject may be pregnant after the subject has been receiving study drug(s), the study drug(s) must immediately be withheld until the result of the pregnancy test is confirmed. If a pregnancy is confirmed, the study drug(s) must be immediately and permanently stopped, the subject must be discontinued from the study, and the Investigator must notify the Study Chair or Medical Monitor within 24 hours of awareness.

Pregnancy should be recorded on a Pregnancy Report Form and reported by the Investigator to the Sponsor or designee in the same timeframe (within 24 hours of awareness) as reporting an SAE.

The Pregnancy should be followed up to 6 months after the end of the pregnancy, which can include birth, spontaneous abortion, or voluntary termination, to collect the outcome with details of the birth, and the presence or absence of any birth defects, congenital abnormalities, or maternal and/or newborn complications, as applicable. Follow-up to a pregnancy should be recorded on a Pregnancy Report Form and should include an assessment of the causal relationship to the study drug and reported by the Investigator to the Sponsor or designee. Pregnancy outcomes must be reported for the female partners of any males who took study drug on the Pregnancy Report Form. Consent to report information regarding these pregnancy outcomes should be obtained from the mother.

Any SAE experienced during pregnancy must be reported on the SAE Report Form. Congenital anomalies/birth defects **always** meet SAE criteria, and should therefore be reported as an SAE using the previously described process for SAE reporting.

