17 APPENDIX A - CONTRACEPTION GUIDELINES

Female Not of Child-bearing Potential are Defined as Follows:

Women are considered post-menopausal and not of child-bearing potential if they have had 12 months of natural (spontaneous) amenorrhea with an appropriate clinical profile (e.g. age appropriate, history of vasomotor symptoms) or 6 months of spontaneous amenorrhea with serum FSH levels > 40 mIU/mL [for US only: and estradiol < 20 pg/mL] or have had surgical bilateral oophorectomy (with or without hysterectomy) at least 6 weeks ago. In the case of oophorectomy alone, only when the reproductive status of the woman has been confirmed by follow-up hormone level assessment is she considered not of child-bearing potential.

Contraception Guidelines for Females of Child-Bearing Potential:

Females of child-bearing potential, defined as all females physiologically capable of becoming pregnant, must use highly effective contraception during the study and for 4 months after the last treatment dose of ublituximab and for at least 30 days after last treatment dose of umbralisib or venetoclax. The highly effective contraception is defined as either:

- 1. True abstinence: When this is in line with the preferred and usual lifestyle of the subject. Periodic abstinence (e.g., calendar, ovulation, symptothermal, post-ovulation methods) and withdrawal are not acceptable methods of contraception.
- 2. Sterilization: have had surgical bilateral oophorectomy (with or without hysterectomy) or tubal ligation at least 6 weeks ago. In case of oophorectomy alone, only when the reproductive status of the woman has been confirmed by follow-up hormone level assessment.
- 3. Male partner sterilization (with the appropriate post-vasectomy documentation of the absence of sperm in the ejaculate). For female subjects on the study, the vasectomised male partner should be the sole partner for that subject.
- 4. Oral contraception, injected or implanted hormonal methods.
- 5. Use of a combination of any 2 of the following (a+b):
 - a. Placement of an intrauterine device (IUD) or intrauterine system (IUS).
 - b. Barrier methods of contraception: Condom or Occlusive cap (diaphragm or cervical/vault caps) with spermicidal foam/gel/film/cream/vaginal suppository.

The following are **unacceptable** forms of contraception for females of child-bearing potential:

- Female condom
- Natural family planning (rhythm method) or breastfeeding
- Fertility awareness
- Withdrawal
- Cervical shield

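### Routine urine pregnancy testing stops at Cycle 15 in Table 5, although Arm B dosing continues past that point with no end cycle

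*Combined protocol and SAP*

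**What the plan says.** **Urine test schedule.** Section 6, Table 5 marks the urine pregnancy test at Cycles 2-3, Cycle 4 Day 1, Cycles 5 and 6, and Cycles 9, 12 and 15. The cell is blank for Cycle 18 and later, and also at end of treatment, the safety follow-up visits, long-term follow-up and end of study. Footnote 18 reads: "For females of childbearing potential. This is only required if patients are receiving drug". The serum test is done once, within 3 days before Cycle 1 Day 1 (footnote 17).

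**Where timing is set.** Section 7 refers back to the tables: "Laboratory assessments will be collected as specified in the study assessments tables". Section 7.1 lists the urine test for Phase 3 women of child-bearing potential and gives no frequency.

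**Dosing.** Arm A's last dosing block is Cycles 7 to 15 (Synopsis; Section 8.3). Arm B's last block is Cycle 7 onward, with umbralisib daily and ublituximab on "Day 1, every 3 cycles (9, 12, 15, 18, etc" (Synopsis; also Section 8.4). Section 4.1 adds: "Subjects will remain on study treatment until the occurrence of definitive disease progression", with completion of treatment, toxicity and withdrawal as the other reasons to stop.

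**Other safeguards.** Appendix A says women of child-bearing potential "must use highly effective contraception during the study and for 4 months after the last treatment dose of ublituximab". Section 12.8 requires study drug to be withheld and a test result confirmed when pregnancy is suspected.

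**The concern.** The two arms share one visit schedule but have different treatment durations. The urine pregnancy row ends where Arm A's treatment ends, yet Arm B continues on the drugs that justified testing up to that point. No reason is given for testing Arm B women at least every third cycle through Cycle 15 and then not at all.

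What is at stake is fetal exposure. The protocol treats that risk as lasting through dosing and beyond, since contraception must continue for 4 months after the last ublituximab dose. Under Section 12.8 a confirmed pregnancy means immediate and permanent discontinuation of study drug, so earlier detection leads directly to action. Once routine tests stop, detection depends on the woman or the investigator suspecting pregnancy.

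**Working it through.** The plan states no figure to reproduce. The check sets the table beside the dosing schedule and counts visits.

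**1. Marks against dosing**

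| Table 5 visit column | Urine test marked | Arm A on drug | Arm B on drug |
|---|---|---|---|
| Cycles 2-3 | yes | yes | yes |
| Cycle 4 Day 1 | yes | yes | yes |
| Cycles 5 and 6 | yes | yes | yes |
| Cycles 9, 12, 15 | yes | yes | yes |
| Cycle 18 and every 3 cycles | **no** | no | **yes** |

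Arm B dosing in the last row is confirmed in Table 5 itself, which marks Arm B ublituximab in that column.

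**2. Is the blank cell read from the right place?** The same column carries Cycle 24 entries on the immunoglobulin row, as footnote 16 requires (baseline, Cycles 12 and 24), and on the MRD row, as footnote 22 requires. Each visit column checked has 18 fields, matching the 18 row labels and headers. A shifted column is therefore unlikely. These checks cannot detect a single mark lost in the text conversion.

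**3. Does other text supply the test?** Footnote 18 limits marked tests to women on drug and sets no frequency. Section 7 defers to the table, Section 7.1 has no timing, and Section 12.8 applies only on suspicion. None of these orders a routine test after Cycle 15.

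**4. Scheduled tests through Cycle 15.** Cycles 2, 3, 4, 5, 6, 9, 12 and 15 give 2 + 1 + 2 + 3 = 8 tests. The longest nominal interval is 3 × 28 = 84 days.

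**5. The untested period.** With 28-day cycles, Day 1 of cycle c is study day 28(c − 1) + 1, counted from Cycle 1 Day 1:

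- Cycle 15: 28 × 14 + 1 = 393 (last scheduled test)
- Cycle 18: 28 × 17 + 1 = 477 (first visit without a test)
- Cycle 27: 28 × 26 + 1 = 729
- Cycle 39: 28 × 38 + 1 = 1065
- Cycle 42: 28 × 41 + 1 = 1149

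Section 11.11.1.1 plans estimates of "the proportion of subjects alive and progression-free at 6, 12, 24, and 36 months", so 24 and 36 months are natural horizons. At 30.4375 days per month:

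- **24 months** = 730.5 days. The visits are Cycles 18, 21, 24 and 27: 4 visits, 0 tests. Time since the last test is 730.5 − 393 = 337.5 days, or 11.1 months.
- **36 months** = 1095.75 days. The visits are Cycles 18, 21, 24, 27, 30, 33, 36 and 39: 8 visits, 0 tests. Cycle 42 falls after the horizon. Time since the last test is 1095.75 − 393 = 702.75 days, or 23.1 months.

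These are nominal dates. They ignore the ±7-day visit window and the up to 7 days allowed between randomization and first dose. Either could move a visit close to a horizon, such as Cycle 27, to the other side of it.

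**The case against.** **A mark may have been lost.** The case rests on one empty cell in a table whose converted text is visibly garbled elsewhere, and the alignment checks would not notice a dropped mark. This stands as a caveat. Nothing positive suggests that a mark was lost, but the cell should be confirmed against the PDF.

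**A blank or short cell in Table 5 does not always mean no test.** The sparse PK row is marked only at Cycle 4, yet footnote 23 and Section 7.2.1 require a later sample. The MRD cell in the Cycle 18 column shows only Cycle 24, yet footnote 22 orders repeats every 6 cycles. In both cases explicit text extends the cell. Footnote 18 does not: it restricts testing and adds no visits. If the sponsor meant testing to continue while on drug, the blank cell contradicts that intent and the same mark resolves it.

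**Safeguards remain, and Phase 2 had fewer tests.** Contraception is mandatory, and Section 12.8 tells women to report a missed or late period. Table 4 (Phase 2) has only the baseline serum test, so routine on-treatment testing is an added precaution. This is fair and limits the seriousness. It does not explain why Phase 3, having adopted routine testing, stops it for women still on the same drugs. Hematology, chemistry and CMV monitoring all continue in the Cycle 18 column.

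**The consequence is small, and 84 days is only nominal.** Both points are accepted. With ±7-day windows the interval from Cycle 9 to Cycle 12 can reach 84 + 14 = 98 days. The 703-day figure describes one hypothetical woman and is not an expected average.

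**Conclusion.** The concern holds as a minor patient-safety gap. As Table 5 reads, Arm B women of child-bearing potential have 8 scheduled urine tests through Cycle 15 and none from Cycle 18, while dosing continues with no end cycle. For a woman still on drug this means 4 untested visits by 24 months (about 338 days since the last test) and 8 by 36 months (about 703 days). Contraception and testing on suspicion remain.

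The conclusion assumes that the blank cell matches the source PDF and that footnote 18 is a restriction and does not order a test at every on-drug visit. The documents do not give the number of women of child-bearing potential in Arm B. It is likely small, because Section 1.1 puts typical onset around 70 years, though eligibility starts at 18 and admits such women. No count is claimed. No endpoint, type I error or power is affected.

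**What to change.** Check the cell against the source PDF. If it is blank, mark the urine pregnancy test in Table 5's column for Cycle 18 and every 3 cycles thereafter, for women of child-bearing potential still receiving study drug. In practice this means Arm B, and footnote 18 already limits the test to women on drug.

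The cost is one mark in the table and one urine test per existing visit for a small number of women. No visits are added. A woman on drug to 36 months would have 8 further tests (Cycles 18 to 39), keeping the nominal 84-day interval used from Cycle 6 onward.
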